**CYCLE \_\_\_\_\_(fill in cycle #)**

DAY	DATE	TIME	# CAPSULES	SYMPTOMS
1		am pm		
2		am pm		
3		am pm		
4		am pm		
5		am pm		
6		am pm		
7		am pm		
8		am pm		
9		am pm		
10		am pm		
11		am pm		
12		am pm		
13		am pm		
14		am pm		
15		am pm		
16		am pm		
17		am pm		
18		am pm		

19		am pm		
20		am pm		
21		am pm		
22		am pm		
23		am pm		
24		am pm		
25		am pm		
26		am pm		
27		am pm		
28		am pm		

28 DAYS IS THE END OF THE CYCLE. YOUR STUDY DOCTOR WILL LET YOU KNOW IF YOU CAN CONTINUE WITH THE NEXT CYCLE.

**APPENDIX C RISKS OF FETAL EXPOSURE, PREGNANCY TESTING  
GUIDELINES AND ACCEPTABLE BIRTH CONTROL METHODS**

**Risks Associated with Pregnancy**

Lenalidomide is structurally related to thalidomide. Thalidomide is a known human teratogenic active substance that causes severe life-threatening birth defects. An embryofetal development study in animals indicates that lenalidomide produced malformations in the offspring of female monkeys who received the drug during pregnancy. The teratogenic effect of lenalidomide in humans cannot be ruled out. Therefore, a risk minimization plan to prevent pregnancy must be observed.

**Criteria for females of childbearing potential (FCBP)**

This protocol defines a female of childbearing potential as a sexually mature woman who: 1) has not undergone a hysterectomy or bilateral oophorectomy or 2) has not been naturally postmenopausal (amenorrhea following cancer therapy does not rule out childbearing potential) for at least 24 consecutive months (i.e., has had menses at any time in the preceding 24 consecutive months).

**Counseling**

For a female of childbearing potential, lenalidomide is contraindicated unless all of the following are met (i.e., all females of childbearing potential must be counseled concerning the following risks and requirements prior to the start of lenalidomide):

- She understands the potential teratogenic risk to the unborn child
- She understands the need for effective contraception, without interruption, 4 weeks before starting study treatment, throughout the entire duration of study treatment, dose interruption and 28 days after the end of study treatment
- She should be capable of complying with effective contraceptive measures
- She is informed and understands the potential consequences of pregnancy and the need to notify her study doctor immediately if there is a risk of pregnancy
- She understands the need to commence the study treatment as soon as study drug is dispensed following a negative pregnancy test
- She understands the need and accepts to undergo pregnancy testing based on the frequency outlined in this protocol
- She acknowledges that she understands the hazards and necessary precautions associated with the use of lenalidomide

The investigator must ensure that for females of childbearing potential:

- Complies with the conditions for pregnancy risk minimization, including confirmation that she has an adequate level of understanding
- Acknowledge the aforementioned requirements

For a female NOT of childbearing potential, lenalidomide is contraindicated unless all of the following are met (i.e., all females NOT of childbearing potential must be counseled concerning the following risks and requirements prior to the start of lenalidomide):

- She acknowledges that she understands the hazards and necessary precautions associated with the use of lenalidomide

Traces of lenalidomide have been found in semen. Male patients taking lenalidomide must meet the following conditions (i.e., all males must be counseled concerning the following risks and requirements prior to the start of lenalidomide):

- Understand the potential teratogenic risk if engaged in sexual activity with a pregnant female or a female of childbearing potential

Understand the need for the use of a condom even if he has had a vasectomy, if engaged in sexual activity with a pregnant female or a female of childbearing potential.

#### Contraception

Females of childbearing potential (FCBP) enrolled in this protocol must agree to use two reliable forms of contraception simultaneously or to practice complete abstinence from heterosexual contact during the following time periods related to this study: 1) for at least 28 days before starting study drug; 2) while participating in the study; 3) during dose interruptions; and 4) for at least 28 days after study treatment discontinuation.

The two methods of reliable contraception must include one highly effective method and one additional effective (barrier) method. FCBP must be referred to a qualified provider of contraceptive methods if needed. The following are examples of highly effective and additional effective methods of contraception:

- Highly effective methods:
  - Intrauterine device (IUD)
  - Hormonal (birth control pills, injections, implants)
  - Tubal ligation
  - Partner's vasectomy
- Additional effective methods:
  - Male condom
  - Diaphragm
  - Cervical Cap

*[Because of the increased risk of venous thromboembolism in patients taking lenalidomide and dexamethasone, combined oral contraceptive pills are not recommended. If a patient is currently using combined oral contraception the patient should switch to one of the effective method listed above. The risk of venous thromboembolism continues for 4 to 6 weeks after discontinuing combined oral contraception. The efficacy of contraceptive steroids may be reduced during co-treatment with dexamethasone.]*

Implants and levonorgestrel-releasing intrauterine systems are associated with an increased risk of infection at the time of insertion and irregular vaginal bleeding. Prophylactic antibiotics should be considered particularly in patients with neutropenia.

#### Pregnancy testing

Medically supervised pregnancy tests with a minimum sensitivity of 25 mIU/mL must be performed for females of childbearing potential, including females of childbearing potential who commit to complete abstinence, as outlined below.

#### **Before starting study drug**

##### *Female Patients:*

FCBP must have two negative pregnancy tests (minimum sensitivity of 25 mIU/mL) prior to starting study drug. The first pregnancy test must be performed within 10 to 14 days prior to the start of study drug and the second pregnancy test must be performed within 24 hours prior to the start of study drug. The patient may not receive study drug until the study doctor has verified that the results of these pregnancy tests are negative.

##### *Male Patients:*

Must practice complete abstinence or agree to use a condom during sexual contact with a pregnant female or a female of childbearing potential while participating in the study, during dose interruptions and for at least 28 days following study drug discontinuation, even if he has undergone a successful vasectomy.

#### **During study participation and for 28 days following study drug discontinuation**

##### *Female Patients:*

- FCBP with regular or no menstrual cycles must agree to have pregnancy tests weekly for the first 28 days of study participation and then every 28 days while on study, at study discontinuation, and at day 28 following study drug discontinuation. If menstrual cycles are irregular, the pregnancy testing must occur weekly for the first 28 days and then every 14 days while on study, at study discontinuation, and at days 14 and 28 following study drug discontinuation.
- At each visit, the Investigator must confirm with the FCBP that she is continuing to use two reliable methods of birth control.
- Counseling about pregnancy precautions and the potential risks of fetal exposure must be conducted at a minimum of every 28 days.
- If pregnancy or a positive pregnancy test does occur in a study patient, study drug must be immediately discontinued.
- Pregnancy testing and counseling must be performed if a patient misses her period or if her pregnancy test or her menstrual bleeding is abnormal. Study treatment must be discontinued during this evaluation.

- Females must agree to abstain from breastfeeding during study participation and for at least 28 days after study drug discontinuation.

*Male Patients:*

- Counseling about the requirement for complete abstinence or condom use during sexual contact with a pregnant female or a female of childbearing potential and the potential risks of fetal exposure to lenalidomide must be conducted at a minimum of every 28 days.
- If pregnancy or a positive pregnancy test does occur in the partner of a male study patient during study participation, the investigator must be notified immediately.

*Additional precautions*

- Patients should be instructed never to give this medicinal product to another person and to return any unused capsules to the study doctor at the end of treatment.
- Female patients should not donate blood during treatment and for at least 28 days following discontinuation of lenalidomide.
- Male patients should not donate blood, semen or sperm during treatment or for at least 28 days following discontinuation of lenalidomide.
- Only enough study drug for 28 days or one cycle of therapy (whichever is shorter) may be dispensed with each cycle of therapy.

**APPENDIX D                    LENALIDOMIDE EDUCATION AND COUNSELING GUIDANCE  
DOCUMENT**

Protocol Number: \_\_\_\_\_

Patient Name (Print): \_\_\_\_\_ DOB: \_\_\_\_ / \_\_\_\_ / \_\_\_\_ (mm/dd/yyyy)

(Check the appropriate box to indicate risk category)

Female:

If female, check one:

- FCBP (Female of childbearing potential): sexually mature female who: 1) has not undergone a hysterectomy (the surgical removal of the uterus) or bilateral oophorectomy (the surgical removal of both ovaries) or 2) has not been naturally postmenopausal (amenorrhea following cancer therapy does not rule out childbearing potential) for at least 24 consecutive months (i.e., has had menses at any time during the preceding 24 consecutive months)
- NOT FCBP

Male:

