**8.1.10 Eligibility and screening**

The Investigator is responsible for keeping a record of all subjects who sign an Informed Consent Form for entry into the study. All subjects will be screened for eligibility. Screening procedures are outlined in Section 2, Schedule of Study Assessments and unless otherwise specified, must take place within 14 days prior to initiation of therapy. Screening pregnancy tests (sensitivity of at least 25 mIU/mL) for women of child-bearing potential must occur 10 to 14 days prior and again  $\leq$  24 hours from initiation of therapy.

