#### 9.3.1 Collection of Specimens.

**Arm A:** For patients treated on Arm A (patients who will receive lenalidomide during cycles 1 and 2), pharmacokinetic assessments of lenalidomide will occur during days 1 and 2 of cycle 2. Samples will be collected at the following time points: prior to dosing (time 0), 0.5, 1, 2, 3, 4.5, and 6 hours after dose administration on day 1 of cycle 2. An additional sample will be obtained prior to lenalidomide ingestion on day 2 of cycle 2 (i.e. 24 hours after the dose is ingested on day 1).

**Arm B:** For patients in Arm B (patients who receive lenalidomide beginning in cycle 4) PK sampling will occur during days 1 and 2 of cycle 5. The sampling times will be consistent with those in Arm A and comprise the following time points: prior to dosing (time 0), 0.5, 1, 2, 3, 4.5, and 6 hours after dose administration on day 1 of cycle 5. An additional sample will be obtained prior to lenalidomide ingestion on day 2 of cycle 5 (i.e. 24 hours after the dose is ingested on day 1).

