### Schedule of Study Assessments: Arm B (Sequential)

Procedure	Screening	Cycle 1	Cycle 2	Cycle 3	Cycle 4 & 5				Cycle 6	Cycle 7+	End of Therapy o	Follow-Up p
					W1	W2	W3	W4				
Clinical Assessment												
Informed Consent	X											
Physical Examination a	X	X	X	X	X	X	X	X	X	X	X	
ECOG Performance Status b	X	X	X	X	X	X	X	X	X	X	X	
Concomitant medications	X	X	X	X	X	X	X	X	X	X	X	
Interval infection history c		X	X	X	X	X	X	X	X	X	X	
Record adverse events		X	X	X	X	X	X	X	X	X	X	
Perform Drug Accountability d	X				X	X	X	X	X	X	X	
Education and Counseling e					X				X	X	X	
Response assessment n					C5					X n	X	X
Laboaratory Studies and Procedures												
ECG	X											
Complete blood count m	X	X	X	X	X	X	X	X	X	X	X	X
Serum chemistries f	X	X	X	X	X	X	X	X	X	X	X	
Urinalysis	X											
Quantitative immunoglobulins	X	X		X	X					Every 6 mo	X g	X
Direct and indirect antiglobulin test	X											
TSH	X										X	
Pregnancy testing g	X				X g	X	X	X	X	X	X	
Bone marrow biopsy h	Optional										X	
Risk stratification studies i	X											
CT scans r	X										X	
Anti-pneumococcal antibody titers		X		X	X							
Treatment												
Allopurinol l					X	X	X	X				
Thromboprophylaxis k					X	X	X	X	X	X		
Dispense Lenalidomide l					X	X	X	X	X	X		
Lenalidomide					X	X	X	X	X	X		
PCV13 administration		X		X								
Correlative Studies												
Pharmacokinetic Studies s					C5 D1,2							
Pharmacodynamic Studies t	X	X			C4 D1,3 C5 D1	C4 D8			X			

- a. Physical examination should include vitals signs, weight, general physical examination (including neurologic examination), measurement of liver and spleen span in centimeters below the costal margin in the anterior axillary line, and bi-dimensional measurement of cervical, supraclavicular, axillary, and inguinal nodes.
- b. See [Appendix A](#).
- c. See [6.3.10](#) for required information to be documented for each episode of infection.
- d. Patient medication diary is reviewed to assess patient compliance on the first day of each cycle in which lenalidomide is administered.

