- e. The Lenalidomide Education and Counseling Guidance Document ([Appendix D](#)) must be completed and signed by a trained counselor at the participating site prior to each dispensing of lenalidomide treatment. A copy of this document must be maintained in the patient records. The Lenalidomide Information Sheet ([Appendix E](#)) will be given to each patient receiving lenalidomide treatment. The patient must read this document prior to starting lenalidomide study treatment and each time they receive a new supply of study drug.
- f. Serum chemistries should include: comprehensive metabolic panel, phosphate, uric acid, and LDH.
- g. Pregnancy tests for females of childbearing potential. A female of childbearing potential (FCBP) is a sexually mature female who: 1) has not undergone a hysterectomy or bilateral oophorectomy; or 2) has not been naturally postmenopausal (amenorrhea following cancer therapy does not rule out childbearing potential) for at least 24 consecutive months (i.e., has had menses at any time in the preceding 24 consecutive months). Pregnancy tests must occur within 10 – 14 days and again within 24 hours prior to initiation of lenalidomide. FCBP with regular or no menstruation must have a pregnancy test weekly for the first 28 days and then every 28 days while on study treatment (including breaks in treatment); at discontinuation of lenalidomide and at Day 28 post the last dose of lenalidomide. Females with irregular menstruation must have a pregnancy test weekly for the first 28 days and then every 14 days while on study treatment (including breaks in treatment), at discontinuation of lenalidomide and at Day 14 and Day 28 post the last dose of lenalidomide (see [Appendix C: Risks of Fetal Exposure, Pregnancy Testing Guidelines and Acceptable Birth Control Methods](#)).
- h. Unilateral bone marrow biopsy and aspirate will be obtained at end of treatment. In addition to routine pathology, aspirate samples should be studied for, interphase cytogenetics, standard CLL FISH panel, CpG stimulated karyotype, and flow cytometry. If patients decline bone marrow biopsy at end of study, these same studies should be done on peripheral blood. If patients demonstrate anti-ROR1 antibody response, a research bone marrow aspirate may be done every 6 months to isolate normal B-cells for correlative studies.

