- i. Risk stratification studies will include serum  $\beta$ 2-microglobulin in addition to tests performed on the screening bone marrow biopsy specimen: IgVH mutational analysis (unless already known), interphase cytogenetics, stimulated karyotype and standard CLL FISH panel.
- j. Allopurinol should be administered beginning 3 days before first lenalidomide administration and continued through the first cycle of lenalidomide treatment in its entirety. Allopurinol can be continued during subsequent cycles at the treating physician's discretion.
- k. Thromboprophylaxis should begin with lenalidomide in patients at high-risk for venous or arterial thromboembolism (see [5.2.3](#)).
- l. Only enough lenalidomide for 28 days or one cycle of study treatment (whichever is shorter) may be provided to the patient each cycle.
- m. CBC is checked on D1 and D8 during the first cycle of lenalidomide exposure and during the second cycle and/or any subsequent cycle in which the dose of lenalidomide has been escalated. CBC should be checked weekly during any subsequent cycle in which the dose of lenalidomide has been reduced for hematologic toxicity.
- n. Response is assessed clinically (CBC, physical examination) after every 2 cycles of lenalidomide treatment beginning with Cycle 3 (Arm A) or Cycle 5 (Arm B), respectively. For patients meeting clinical criteria for CR for  $\geq$  2 months, bone marrow biopsy and CT scans should be performed to confirm response.
- o. The End of Therapy visit is defined as that occurring after 24 cycles. Patients discontinuing treatment at other times secondary to toxicity, progression, or preference only need the clinical assessment (except informed consent and education and counseling) and a complete blood count. Patients discontinuing for any reason are followed for at least 30 days to ensure resolution of any adverse events; however, these patients will still be followed for outcome until meeting criteria outlined in footnote "p" below.
- p. Patients no longer receiving active treatment are followed every 3 months during the first year and every 6 months thereafter until the patient receives a new CLL therapy, withdrawal of consent, or death.
- q. Unless completed within the last month.
- r. CT scans of the chest, abdomen, and pelvis.

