**Do Not Dispense study drug if:**

- The patient is pregnant.
- No pregnancy tests were conducted for a FCBP.
- The patient states she did not use TWO reliable methods of birth control (unless practicing complete abstinence of heterosexual intercourse) [at least 28 days prior to treatment, during treatment, and during dose interruption].

1. I verified that the required pregnancy tests performed are negative.
2. I counseled FCBP regarding the following:
  - Potential risk of fetal exposure to lenalidomide: If lenalidomide is taken during pregnancy, it may cause birth defects or death to any unborn baby. Females are advised to avoid pregnancy while taking lenalidomide. The teratogenic potential of lenalidomide in humans cannot be ruled out. FCBP must agree not to become pregnant while taking lenalidomide.
  - Using TWO reliable methods of birth control at the same time or complete abstinence from heterosexual contact [at least 28 days prior to treatment, during treatment, during dose interruption and 28 days after discontinuation of lenalidomide].
  - That even if she has amenorrhea she must comply with advice on contraception

- Use of one highly effective method and one additional method of birth control AT THE SAME TIME. The following are examples of highly effective and additional effective methods of contraception:
  - Highly effective methods:
    - Intrauterine device (IUD)
    - Hormonal (birth control pills, injections, implants)
    - Tubal ligation
    - Partner's vasectomy
  - Additional effective methods:
    - Male condom
    - Diaphragm
    - Cervical Cap
- Pregnancy tests before, during, and after treatment, even if the patient agrees not to have reproductive heterosexual contact. Two pregnancy tests will be performed prior to receiving study drug, one within 10 to 14 days and the second within 24 hours of the start of study drug.
- Frequency of pregnancy tests to be done:
  - Every week during the first 28 days of this study and a pregnancy test every 28 days during the patient's participation in this study if menstrual cycles are regular or every 14 days if cycles are irregular.
  - If the patient missed a period or has unusual menstrual bleeding.
  - When the patient is discontinued from the study and at day 28 after study drug discontinuation if menstrual cycles are regular. If menstrual cycles are irregular, pregnancy tests will be done at discontinuation from the study and at days 14 and 28 after study drug discontinuation.

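### The pregnancy-testing passages contradict each other on when Arm B's weekly tests run, on where its pre-lenalidomide test is scheduled, and on whether patients who stop off-schedule need a discontinuation test

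*Combined protocol and SAP*

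**What the plan says.** Arm B is described in Section 9.3.1 as "patients who receive lenalidomide beginning in cycle 4". Table 2 agrees, and Section 5.1.1 sets the cycle length at 28 days. Arm B protocol therapy itself begins with vaccine on Cycle 1 Day 1 (Table 3).

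**Weekly tests.** Three texts and one grid bear on this:
- Appendix C, on testing during participation: "FCBP with regular or no menstrual cycles must agree to have pregnancy tests weekly for the first 28 days of study participation".
- Appendix D, the counselling form completed before each dispensing: "Every week during the first 28 days of this study".
- Section 10, footnote g: women with regular or no menstruation "must have a pregnancy test weekly for the first 28 days and then every 28 days while on study treatment". The event that starts those first 28 days is not named.
- Section 10, Arm B calendar: a test at Screening, none in Cycles 1-3, then each of weeks 1-4 in the combined column for Cycles 4 and 5.

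**Pre-drug tests.** Section 3.1.10, the counselling text in Section 8.1, footnote g, Appendix C and Appendix D all call for one test 10-14 days before lenalidomide or study drug and one within 24 hours of it. Section 8.1 and Appendix C add that drug is withheld until both are verified negative. Section 8.1.10 uses another anchor. It says "Screening pregnancy tests (sensitivity of at least 25 mIU/mL) for women of child-bearing potential must occur 10 to 14 days prior", counted from the initiation of therapy, and does not say which therapy.

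**Discontinuation tests.** Footnote g requires a test "at discontinuation of lenalidomide and at Day 28 post the last dose of lenalidomide", with a further Day 14 test if menstruation is irregular. Appendices C and D also require a test at discontinuation, which they word as leaving the study, and the same post-drug tests. Footnote o says that patients stopping at times other than the 24-cycle visit, for toxicity, progression or preference, "only need the clinical assessment (except informed consent and education and counseling) and a complete blood count".

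**The concern.** Section 8.1 says that a teratogenic effect of lenalidomide in humans cannot be ruled out and calls for a risk-minimisation plan. That plan works only if every page gives staff the same test dates. Counting from study entry and counting from first lenalidomide dose give the same dates in Arm A, where the two events coincide, but not in Arm B, where they are 84 days apart. Two coordinators working from different pages would test the same Arm B woman on different days. One working from the calendar alone would find no slot for a test that five other places require. At the end of treatment, one following footnote o would omit a test that another following footnote g would do. What is at stake is delivery of a safety procedure as described, not any efficacy estimate.

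**Working it through.** The plan states no figure to reproduce. The check is day arithmetic with 28-day cycles, counting Cycle 1 Day 1 as study day 1, followed by a comparison of passages.

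1. **First lenalidomide dose, Arm B.** 3 × 28 + 1 = study day 85 (Cycle 4 Day 1).

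2. **Weekly block on the Appendix C and D clock.** Days 1-28. Days 29 to 84 lie between its end and the first dose: 84 − 28 = 56 full days.

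3. **Window for the 10-14 day pre-drug test.** 85 − 14 = 71 and 85 − 10 = 75. Cycle 3 starts on day 57, so the window is Cycle 3 Day 15 to Day 19. The Arm B calendar has no pregnancy-test entry there.

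4. **What the Appendix C clock alone would give.** Assume weekly tests on days 1, 8, 15 and 22. Appendix C does not say whether the later interval counts from day 22 or day 29, so both are shown. The first 28 days on lenalidomide are days 85-112.

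| Menses | Later tests | In days 71-75 | In days 85-112 |
|---|---|---|---|
| Regular or none | every 28 days from day 22: 50, 78, 106 | none | one (106) |
| Regular or none | every 28 days from day 29: 29, 57, 85, 113 | none | one (85) |
| Irregular | every 14 days from day 22: 36, 50, 64, 78, 92, 106 | none | two (92, 106) |
| Irregular | every 14 days from day 29: 29, 43, 57, 71, 85, 99 | one (71) | two (85, 99) |

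The Arm B calendar shows four tests in days 85-112, one in each of weeks 1-4 of Cycle 4. The two sources therefore differ by two or three tests in the first 28 days on drug. The separately required test within 24 hours before the first dose is not counted in this comparison.

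5. **Section 8.1.10.** If initiation of therapy means lenalidomide, the section agrees with the other five places. If it means protocol therapy, Arm B's tests attach to the first vaccine dose on day 1. The wording allows either.

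6. **Footnotes g and o.** Both calendars list pregnancy testing under laboratory studies and procedures, not under clinical assessment. Footnote o keeps the clinical assessment and adds only a blood count, so the discontinuation pregnancy test drops out of what it lists. Footnote g and Appendices C and D carry no matching exception. Section 5.3 allows therapy beyond 24 cycles, so stopping at other times can mean later as well as earlier.

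**The case against.** The strongest reply is that the safeguards stand whatever the grid shows. Five places tie the pre-drug tests to lenalidomide or study drug, and two of them bar drug until both results are verified negative. The note opening Section 8 also requires a negative test before dispensing, and Appendix D has the counsellor confirm that the required tests were negative. In the Arm B calendar the Cycle 4 week 1 entry carries its own footnote g mark, which points to the pre-drug rule. Section 8.1.10 sits inside the lenalidomide section, so its therapy may well mean lenalidomide. All of this stands, and it rules out three stronger readings that a reader might infer:

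- *That Arm B women have their pre-drug test 84-98 days early.* The screening test does fall 3 × 28 = 84 to 84 + 14 = 98 days before lenalidomide. It is a mistimed pre-drug test only if a site counts it as the 10-14 day test. Nothing directs that, and it can equally be an extra baseline test.
- *That patients who stop off-schedule are excused from the discontinuation test.* Footnote o omits the test, but footnote g and both appendices still require it. This is a contradiction, and no rule says that footnote o prevails. Footnote o does not mention the later Day 14 and Day 28 tests.
- *That counselling comes too late in Arm B.* The first counselling mark falls in the first week of lenalidomide in both arms because footnote e ties it to dispensing. The 28-day contraception lead-in is set separately in Section 3.1.10.

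The reply does not remove the conflict itself. A bar on dispensing does not create a visit in Cycle 3, and it does not settle which weekly schedule or which footnote a site should follow.

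**Conclusion.** The inconsistency is real and limited to three places. The weekly-test clock in Appendices C and D disagrees with the Arm B calendar, and footnote g does not settle it. The Arm B calendar has no entry where five other places put a pre-drug test, and Section 8.1.10 is ambiguous for that arm. Footnote o omits a test that footnote g and both appendices require. No text waives the pre-drug test. A site would reach Cycle 4 Day 1 without it only by relying on the calendar, or on one reading of Section 8.1.10, alone.

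The number of women affected cannot be worked out. Section 3.4 plans 24 women among 48 patients, but the share of childbearing potential is not given. Section 9 refers to a low number of patients still receiving treatment, so the Arm B start-up conflicts may have little forward effect. The footnote conflict applies to any woman of childbearing potential still on drug. The primary endpoint, sample size and type I error are unaffected. The day counts assume undelayed 28-day cycles.

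**What to change.** Reconcile Section 8.1.10, the Arm B calendar row, footnotes g and o, and the testing text in Appendices C and D, as follows:
- Count every test from one named event and give one schedule per arm.
- Make the Arm B calendar and the pre-drug testing text agree.
- Say in Section 8.1.10 which therapy is meant.
- State how footnotes g and o apply together when a patient stops at a time other than the 24-cycle visit.

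Which schedule governs is for the sponsor to decide; this review does not choose between them. The cost is amendment wording in one subsection, one calendar row, two footnotes and two appendices. Any added or dropped test contact depends on the schedule chosen. No statistical section needs to change.
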